4.1.1 Primary Safety Endpoints

The primary safety endpoints include the following:

- 1. Incidence of adverse events through Day 365.
- 2. Change from Baseline in clinical chemistry, hematology, u/a at Days 15, 28, 59, 91, 180 and 365.
- 3. Injection site reactions, as measured by assessments at Days 1, 8, 15, 21, 28, and 59 using National Cancer Institute's Common Terminology for Adverse Events v3.0 criteria as follows:

Grade 1=Pain, itching, erythema;

Grade 2=Pain or swelling with inflammation or phlebitis;

Grade 3=Ulceration or necrosis that is severe or operative intervention indicated.

4. Clinically significant changes in physical examination from Baseline at Days 15, 28, 59, 91, 180 and 365.

Secondary Efficacy Endpoints

The Secondary Efficacy endpoints include the following:

- 1. Change from Baseline in hemodynamic measurements (Appendix B: ABI, TBI, and Wave Form Analysis) and TcPO₂ at Days 15, 28, 59, 91, 180 and 365.
- 2. Change from Baseline in subject-assessed pain, as measured by the VAS (Appendix C) at Days 15, 28, 59, 91, 180 and 365.
- 3. Change from Baseline in ulcer area, in square millimeters, as assessed by digital photograph and measurement of the largest contiguous ulcerated area, at Days 15, 28, 59, 91, 180 and 365.

Pharmacokinetic Evaluations

Pharmacokinetics of VM202 will be assessed using blood VM202 DNA concentration levels from samples obtained pre-dose at the first dose administration (Day 1). In addition, levels will be measured at Days 21, and 59 (if DNA is detected at Day 21).

Pharmacodynamic Evaluations

Pharmacodynamics will be assessed as the change from Day 1 in serum HGF level at Days 8, 15, 21 and 59. Potential immune response to HGF will be assessed as change

from Day 1 in level of neutralizing antibodies (anti-HGF antibodies) at Days 15, 28, 59 and 180. The ability of HGF to stimulate cell growth will be assessed as the change from Baseline in level of endothelial progenitor cell assay at Days 15, 28, 59 and 180.

Overall Study Design

The overall trial design includes: 1) a multi-dose Phase I safety and tolerability evaluation; 2) a preliminary efficacy, pharmacokinetic and pharmacodynamic evaluation; and 3) a safety review between dosing cohorts in order to meet defined safety criteria. The study will evaluate vascular assessments as primary measures of efficacy and adverse event collection and laboratory parameters as the primary monitored measures of safety (see Table 4-1).

Study Population

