Protocol Synopsis: Study Design (C) Formerly: After all subjects in the first dose cohort have completed the 30-day (± 2 days) follow-up visit following the 1st dose of study drug, an interim safety evaluation will be performed with the submission of safety data to the Data Safety Monitoring Committee (DSMC). If the DSMC recommends continuing the study, the second dose cohort will be treated. Modified to: After the first subject in each cohort completes day 30 (± 2 days), subsequent to day 15 dosing of the other 2 subjects in the same cohort, an interim safety evaluation will be performed with the submission of safety data to the Data Safety Monitoring Committee (DSMC). If the DSMC recommends continuing the study, the next dose cohort will be treated.	xii	The cumulative safety of VM202 demonstrated in the first 2 cohorts allows advancement to future cohorts in a prudent and expeditious timeframe.

Type of Modification to Protocol	Affected	Reason(s) for the
(A: Added, C: Changed, D: Deleted)	Pages	Modification(s)
Protocol Synopsis: Procedures (C) Formerly: After all subject in each dose cohort have completed the Day -30 (+ 2 days) follow-up visit, an interim safety evaluation will be performed with the submission of data to the DSMC. Modified to: After the first subject in each dose cohort have completed the Day -30 (+ 2 day) follow-up visit and subsequent to day 15 dosing of the other subjects in the same cohort an interim safety evaluation will be performed with the submission of data to the DSMC.	xiv	The cumulative safety of VM202 demonstrated in the first 2 cohorts allows advancement to future cohorts in a prudent and expeditious timeframe.
Sample Size and Power (C) Formerly: This is a Phase I, Dose-Escalation, Single Center Study. Modified to: This is a Phase I, Dose-Escalation Study.	XV	Changed to allow the option to use multi -centers to increase patient enrollment.
Protocol Synopsis: Pharmacokinetics (C) Formerly: Pharmacokinetic evaluation will determine AUC ₀₋₈ , C _{max} , T _{max} , T _{1/2} for all 4-dose levels of VM202 DNA Modified to: Descriptive statistics (N, mean, median, SD, minimum and maxium values, where applicable) of VM202 DNA levels will be reported.	XV	VM202 disappears from the body 4 hours after injection. Analysis can not be done.

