Section 3.2 Secondary Objectives (C) Formerly: To evaluate the change in VM202 DNA levels from Day 1 to Day 59. Modify to: To evaluate the change in VM202 DNA levels from Day 1 to Day 21.	5	Changed to account for eliminated laboratory test
Section 4.1.3 Pharmacokinetic Evaluations (D) Formerly: Pharmacokinetics of VM202 will be assessed using blood VM202 DNA concentration levels from samples obtained pre-dose and 60 minutes post-dose at the first and second dose administration (Day 1 and Day 15). In addition, levels will be measured at Days 8 , 21, 28 and 59.	6	Deleted laboratory test

Type of Modification to Protocol (A: Added, C: Changed, D: Deleted)	Affected Pages	Reason(s) for the Modification(s)		
Modify to: Pharmacokinetics of VM202 will be assessed using blood VM202 DNA concentration levels from samples obtained pre-dose at the first dose administration (Day 1). In addition, levels will be measured at Days 21 and 59 (if DNA is detected at day 21).				
Section 4.1.4 Pharmacodynamic Evaluations (D) Formerly: Pharmacodynamics will be assessed as the change from Day 1 in serum HGF level at Days 8, 15, 21, 28 and 59. Modify to: Pharmacodynamics will be assessed as the change from Day 1 in serum HGF level at Days 8, 15, 21 and 59.	6	Deleted laboratory test		
4.2.3 Number of Study Subjects (C) Formerly: There will 12-15 subjects selected at one site for participation in this study with 3 subjects treated in each of four (4) study cohorts. Modify to: There will 12-15 subjects selected for participation in this study with 3 subjects treated in each of four (4) study cohorts.	7	Changed to allow the option to use multi -centers to increase patient enrollment.		

	Type of Modification to Protocol (A: Added, C: Changed, D: Deleted) Section 4.1 Study Procedures Chart (C) Formerly:													Reason(s) for Modification(
														Deleted laborate tests	
	Screen / Baseline						Т	reatment Pe	riod		1		1		
		Firs	First Dose Follow-Up Second Dose 2 nd Follow-Up ⁶												
	Day -30 to Day	Day 1 pre-dose	Day 1 post-dose	Day 8 (+/- 2days)	Day 15 Pre dose (+/- 3 days)	Day15 Post-dose	Day 16	Day 21 (+/- 3 days)	Day 28 (+/- 3 days)	Day 59 (+/- 7 days)	Day 91 (+/- 7 days)	Day 180 (+/- 10 days)	Day 365 (+/- 10 days)	Unscheduled Visit	Early Termination
Consent Form	X														
Confirm Eligibility		X													
Medical History	X														
Chest X-ray or CT scan of chest ¹	X												X		X
Physical Exam	X				X				X	X	X	X	X	X	X

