2.2 Secondary Objectives

The secondary objectives of the study will include the following exploratory evaluations:

- To investigate the effects of the intramuscular VM202 to improve pain at rest and/or to heal ischemic ulcers of the affected limb. The VAS assessment tool will be used for this evaluation:
- To evaluate the anatomic and physiological extent of collateral vessel development in subjects with critical limb ischemia as measured by MRA;
- To evaluate the change in serum HGF levels from Day 1 to Day 59;
- To evaluate the change in VM202 DNA levels from Day 1 to Day 59;
- To evaluate the immune response to HGF in subjects with CLI as measured by the change in anti-HGF antibodies from Day 1;
- To evaluate the ability of VM202 to stimulate endothelial progenitor cells as measured by the change in endothelial cell progenitor assay levels from screening to Day 59.

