11. PHARMACOKINETICS

VM202 DNA levels will be determined before dose on Day 1. In addition, VM202 DNA levels will be collected on Day 21 and Day 59 (if DNA is detected on Day 21). VM202 DNA level results will be summarized using descriptive statistics at baseline and at each post baseline time point. Changes from baseline will also be summarized.

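### VM202 DNA sampling can show whether plasmid persists but not pharmacokinetics, so Table 25 should report detection counts in place of mean, SD and change from baseline

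*SAP*

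**What the plan says.** The current protocol and the SAP agree on the sampling times. Under Pharmacokinetic Evaluations in Protocol 4.1, DNA is measured in "samples obtained pre-dose at the first dose administration (Day 1"), and then "levels will be measured at Days 21, and 59 (if DNA is detected at Day 21"). Table 4-1 and SAP 11 give the same schedule.

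For analysis, SAP 11 states: "VM202 DNA level results will be summarized using descriptive statistics at baseline and at each post baseline time point". It adds changes from baseline. The Table 25 shell has N, mean (SD), median, minimum and maximum, with Result and Change columns, for baseline, Day 21 and Day 59. Its unit is a placeholder, and it has no detected/tested count and no detection limit. Protocol 9.3 and the synopsis call for the same kind of descriptive statistics, where applicable.

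The objectives differ. SAP 2.2 reads "To evaluate the change in VM202 DNA levels from Day 1 to Day 59", whereas Protocol 3.2 ends the comparison at Day 21.

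Two entries in the Version 5.0 part of Protocol Appendix E give background. The reason for replacing AUC, Cmax, Tmax and half-life with descriptive statistics is "VM202 disappears from the body 4 hours after injection. Analysis can not be done". The sampling text replaced at that version had required samples "pre-dose and 60 minutes post-dose at the first and second dose administration (Day 1 and Day 15"), with Day 59 among the further times and no condition on Day 21. The same version refers to "The cumulative safety of VM202 demonstrated in the first 2 cohorts", so two cohorts had apparently been dosed before it took effect.

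**The concern.** A pharmacokinetic summary needs at least one sample taken while drug may be in the blood. Here one sample precedes all drug. The others come, at nominal timing, long after the point at which the sponsor says the drug has gone. The planned statistics would then be averages of results mostly or wholly below the assay limit, under a heading that promises kinetics.

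The samples do bear on a useful question: is plasmid still detectable about a week after the second dose? That matters for a gene-transfer product, and the Version 6.0 entries in Appendix E cite the absence of long-term plasmid persistence when shortening follow-up. Table 25 does not present the result in a form that answers it. At Day 59 the summary is also conditioned on an earlier positive result, and nothing in the shell warns the reader.

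**Working it through.** **Inputs.** Doses on Days 1 and 15 (Protocol 4.6). Day 15 ± 3, Day 21 ± 3 and Day 59 ± 7 days (Table 4-1). Stated disappearance at 4 hours (Appendix E, Version 5.0). Four cohorts of 3 (SAP 3). The 4-hour figure cannot be reproduced: the documents give no concentrations, half-life or assay limit behind it. It is taken as the sponsor's statement.

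**Timing after the second dose.**

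| Sample | Nominal gap | Multiple of 4 h | Gap at window limits |
|---|---|---|---|
| Day 21 | (21 − 15) × 24 = 144 h | 144/4 = 36 | 18 − 18 = 0 to 24 − 12 = 12 days |
| Day 59 | (59 − 15) × 24 = 1056 h | 1056/4 = 264 | 52 − 18 = 34 to 66 − 12 = 54 days |

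A gap near zero at Day 21 needs both visits at opposite ends of their windows. At nominal timing no post-dose sample falls within 4 hours.

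**Change column.** Change = post-dose value − pre-dose value. If no subject carries the plasmid before dosing and the assay gives no false positive, the second term is 0 and Change repeats Result.

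**Mean and SD.** SAP 11 has no rule for a result below the detection limit; SAP 8.3 says only that missing values are not imputed. Suppose one of three subjects has a detectable value c. The mean is (c + 0 + 0)/3 = c/3 if non-detects are set to zero, and c if they are left out. The reported mean differs threefold by an unstated convention.

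**What a detection count would say.** For 0 detected of n, the exact one-sided 95% upper limit is 1 − 0.05^(1/n), and the two-sided 95% upper limit is 1 − 0.025^(1/n).

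| n | One-sided | Two-sided |
|---|---|---|
| 3 (one cohort) | 63.2% | 70.8% |
| 12 (pooled) | 22.1% | 26.5% |
| 15 (pooled, one cohort expanded) | 18.1% | 21.8% |

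If plasmid were detectable at Day 21 in an assumed 5% of subjects, the chance of at least one detection in 12 is 1 − 0.95^12 = 46%. At an assumed 10% it is 1 − 0.90^12 = 72%. So the sample carries some, though limited, information on persistence.

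**Day 59.** Under current text a Day 59 value exists only after a positive Day 21. Under the text in force before Version 5.0 it was unconditional. If Cohorts I and II followed the earlier text, the Day 59 row would put unselected subjects (2 and 4 mg) beside subjects selected as positive (8 and 16 mg).

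**60-minute samples.** If the earlier schedule was followed in Cohorts I and II, 2 cohorts × 3 subjects × 2 doses = 12 samples were planned at 60 minutes. They would be the only ones inside the 4-hour period.

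**The case against.** The best defence is that the sponsor dealt with this openly. The 4-hour remark is the stated reason for giving up kinetic parameters, Protocol 2.0 leaves pharmacokinetics to future trials, the objective is listed as exploratory, and making Day 59 depend on Day 21 is already a persistence rule. With 3 subjects per cohort, an all-negative result would be plain from the listing, and a limit of 63% says little. Most of this stands as a reason to treat the point as modest. It does not rescue mean, SD and change as the tabulated result, nor supply the missing count, detection limit or Day 59 condition.

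A reader might infer that the SAP leaves out the 60-minute samples and so discards the only exposure data. The documents do not support that. The programmer note to Table 25 asks for every available time point, Listing 26 prints DNA levels with collection date and time, and SAP 4 requires pharmacokinetic data to be listed by subject. Any such value could be captured. The 60-minute requirement is superseded text, its absence from the current schedule is not an error, and nothing confirms that the samples were drawn or assayed. What remains is that SAP 11 does not name them or say how they would be summarised. The same general note appears on other shells, so two programmers could build different tables.

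A reader might also infer that the plan compares zero with zero, or tabulates assay noise. That goes too far. The Day 1 sample is taken before any plasmid is given, the documents say nothing about assay precision, and a positive Day 21 result would be a real finding.

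**Conclusion.** The point holds as one of analysis and labelling. At nominal timing both post-dose samples lie far beyond the sponsor's own 4-hour figure (36 and 264 times), so they can address persistence and not pharmacokinetics. Mean, SD and change from baseline do not convey a persistence result, and the Day 59 row is conditional on a positive Day 21 without saying so. The mismatch between SAP 2.2 and Protocol 3.2 is a plain inconsistency.

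This rests on the 4-hour statement, for which no data are shown, and on visits near their nominal days. The mixing of Day 59 values further assumes that Cohorts I and II had their Day 59 draws under the earlier text; Appendix E suggests this but does not prove it. The primary safety objective, dose escalation and the MTD are unaffected.

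**What to change.** - Label the objective persistence of VM202 DNA, and align SAP 2.2 with the Day 21 end point in Protocol 3.2.
- In SAP 11 and Table 25, replace mean, SD and change with number detected over number tested at Day 21, by dose and pooled. Give exact confidence limits, stating whether one- or two-sided, and the assay detection limit.
- Footnote that Day 59 is drawn only after detection at Day 21, and mark any Day 59 values obtained without that condition.
- State in SAP 11 that any 60-minute post-dose values collected in Cohorts I and II under earlier protocol versions will be summarised separately by dose as exposure data. Listing 26 needs no change.
- Make matching edits to Protocol 4.1, Protocol 9.3 and the synopsis; otherwise the SAP would contradict the descriptive statistics named there.

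The cost is one table shell and wording in both documents, including a protocol amendment for the text changes, with no new sample. The downside is that the study no longer claims pharmacokinetics for the higher doses. Any exposure summary would cover 2 mg and 4 mg only, and only if the early samples exist.

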12. PHARMACODYNAMICS

An endothelial progenitor cell assay test will be performed at Screening, Day 1 (Post Dose), Day 15 (Post Dose), Day 28, Day 59, Day 180 and Day 365. Endothelial progenitor cell assay test results will be summarized using descriptive statistics at baseline and at each post baseline time point. Changes from baseline will also be summarized.

Serum HGF levels will be collected at Day 1 (Pre-Dose), Day 8, Day 15 (Pre-Dose), Day 21 and Day 59. Results and changes from baseline will be presented by time point.

Anti-HGF antibodies data will be collected on Day 1 (Pre-Dose), Day 15 (Pre-Dose), Day 59 and possibly Day 180. Results will be presented in listings.

APPENDIX A: LIST OF TABLES AND LISTINGS

List of Tables

| Table | |
|--------|---|
| Number | Table Description |
| 1 | Subject Disposition |
| 2 | Demographic Characteristics (ITT/Safety Population) |
| 3 | Abnormal Medical History at Baseline (Safety Population) |
| 4 | Peripheral Vascular Disease Intervention History (Safety Population) |
| 5 | Ulcer Measurement (ITT Population) |
| 6 | Ankle Brachial-Index (ITT Population) |
| 7 | Toe Brachial-Index (ITT Population) |
| 8 | Visual Analogue Scale for Pain (ITT Population) |
| 9 | Transcutaneous Oxygen Pressure Assessment- TcPO ₂ (ITT Population) |
| 10 | Subject Analgesic Use (ITT Population) |
| 11 | Study Drug Exposure(Safety Population) |
| 12 | Treatment Emergent Adverse Events by Cohort (Safety Population) |
| 13 | Treatment Emergent Adverse Events by System Organ Class and Severity |
| | (Safety Population) |
| 14 | Treatment Emergent Adverse Events by System Organ Class and |
| | Relationship to Study (Safety Population) |
| 15 | Treatment Emergent Serious Adverse Events by Cohort (Safety |
| 161 | Population) |
| 16.1 | Hematology (Safety Population) |
| 16.2 | Chemistry (Safety Population) |
| 16.3 | Urinalysis (Safety Population) |
| 17.1 | Hematology – Shift from Baseline (Safety Population) |
| 17.2 | Chemistry – Shift from Baseline (Safety Population) |
| 17.3 | Urinalysis – Shift from Baseline (Safety Population) |
| 18 | Physical Examinations- Shift from Baseline (Safety Population) |
| 19 | Vital Signs (Safety Population) |
| 20 | Retinal Fundoscopy- Shift from Baseline (Safety Population) |
| 22 | Infection Tests (Safety Population) |
| | Tumor Markers (Safety Population) |
| 23 | Injection Site Reaction (Safety Population) |
| 24 | Concomitant Medications (Safety Population) |

List of Tables (cont)

| Table | |
|--------|--|
| Number | Table Description |
| 25 | VM202 DNA Levels (ITT Population) |
| 26 | Endothelial Progenitor Cell Assay (ITT Population) |
| 27 | Serum HGF Levels (ITT Population) |

List of Data Listings

| Listing | | CRF |
|---------|--|------------|
| Number | Listing Description | Plate(s) |
| 1 | Subject Disposition (including Informed Consent | Derived,1, |
| | Date/Investigator Signature) | 100 |
| 2 | Inclusion/ Exclusion Criteria | 1-3 |
| 3 | Demographics/ 12-Lead ECG Results | 4,9 |
| 4 | Medical History | 5 |
| 5 | Peripheral Vascular Disease Intervention History | 6 |
| 6 | Serum/Urine Pregnancy Test/ Mammogram/ Pap Smear | 4,15,19,24 |
| | Results/ Pregnancy Outcome | |
| 7 | Ulcer Measurements | 16 |
| 8 | High Resolution MRA/ Injection Site Reaction | 16 |
| 9 | Assessment of CLI | 17 |
| 10 | Hemodynamic Assessments | 18 |
| 11 | Visual Analogue Scale for Pain | 19 |
| 12 | Transcutaneous Oxygen Pressure Assessment- TcPO ₂ | 19 |
| 13 | Concomitant Medications Identified as being Analgesic in | 98 |
| | Nature | |
| 14 | Study Drug Administration | 20 |
| 15 | Adverse Events | 97 |
| 16 | Serious Adverse Events | 97 |
| 17 | Hematology | 11 |
| 18 | Chemistry | 12 |
| 19 | Urinalysis | 13 |
| 20 | Physical Examinations | 7,8 |
| 21 | Vital Signs | 9 |
| 22 | Retinal Fundoscopy/ Chest X-Ray/ CT Scan | 10 |
| 23 | Infection Tests | 14 |
| 24 | Tumor Markers | 15 |
| 25 | Concomitant Medications | 98 |
| 26 | VM202 DNA Levels (include Collection Date/Time from CRF) | 16, Lab |
| 27 | Endothelial Progenitor Cell Assay | 14 |
| 28 | Serum HGF/ Anti HGF Antibodies (include Collection | 14, Lab |
| | Date/Time from CRF) | |
| 29 | Telephone Follow-Up Contact | 22 |
| 30 | Waiver | 23 |

List of Data Listings (cont)

| Listing | | CRF |
|---------|---------------------|----------|
| Number | Listing Description | Plate(s) |
| 31 | Death | 101 |

APPENDIX B: TABLE LAYOUTS

Viromed Co., Ltd. Page 1 of x Protocol Number: US-06-1-001

Table 1 **Subject Disposition** All Subjects

| | VM202- 2 mg | VM202- 4 mg | VM202-8 mg | VM202- 16 mg |
|--|-------------|-------------|------------|--------------|
| Subjects Enrolled | n | n | n | n |
| Safety Population [1] | n | n | n | n |
| ITT Population [2] | n | n | n | n |
| Received 2 Doses of VM202? | | | | |
| Yes | n (%) | n (%) | n (%) | n (%) |
| No | n (%) | n (%) | n (%) | n (%) |
| Last Visit Completed | | | | |
| Any Visit Prior to Visit- Day 21 | n (%) | n (%) | n (%) | n (%) |
| Visit- Day 21 | n (%) | n (%) | n (%) | n (%) |
| Visit- Day 28 | n (%) | n (%) | n (%) | n (%) |
| Visit- Day 59 | n (%) | n (%) | n (%) | n (%) |
| Visit- Day 91 | n (%) | n (%) | n (%) | n (%) |
| Visit- Day 180 | n (%) | n (%) | n (%) | n (%) |
| Visit- Day 365 | n (%) | n (%) | n (%) | n (%) |
| Completed Study? | | | | |
| Yes | n (%) | n (%) | n (%) | n (%) |
| No | n (%) | n (%) | n (%) | n (%) |
| Primary Reason for Discontinuation | | | | |
| Screen failure | n (%) | n (%) | n (%) | n (%) |
| Lost to Follow-up | n (%) | n (%) | n (%) | n (%) |
| Adverse Event | n (%) | n (%) | n (%) | n (%) |
| Non-compliance | n (%) | n (%) | n (%) | n (%) |
| Subject withdrew consent | n (%) | n (%) | n (%) | n (%) |
| Principal Investigator decision | n (%) | n (%) | n (%) | n (%) |
| Subject requires intervention for treatment of acute limb ischemia | n (%) | n (%) | n (%) | n (%) |
| Other | n (%) | n (%) | n (%) | n (%) |

^{*} Percentages based on number of subjects Enrolled.
[1] All subjects who received at least one dose of study drug.

^[2] All subjects who received at least one dose of study drug and had at least one post dose assessment.

Table 2
Demographic Characteristics
ITT Population

| | VM202- 2 mg (N=) | VM202- 4 mg (N=) | VM202- 8 mg (N=) | VM202- 16 mg (N=) |
|---|----------------------|----------------------|----------------------|-----------------------|
| Age (years) [1] | | | | |
| N | n | n | n | n |
| Mean (SD) | xx.x (xx.xx) | xx.x (xx.xx) | xx.x (xx.xx) | xx.x (xx.xx) |
| Median | XX.X | xx.x | XX.X | xx.x |
| Min, Max | xx, xx | xx, xx | xx, xx | xx, xx |
| Sex | | | | |
| Male | n (%) | n (%) | n (%) | n (%) |
| Female | n (%) | n (%) | n (%) | n (%) |
| Ethnicity | | | | |
| Hispanic or Latino | n (%) | n (%) | n (%) | n (%) |
| Not Hispanic or Latino | n (%) | n (%) | n (%) | n (%) |
| Race | | | | |
| American Indian or Alaska Native | n (%) | n (%) | n (%) | n (%) |
| Asian | n (%) | n (%) | n (%) | n (%) |
| Black or African American | n (%) | n (%) | n (%) | n (%) |
| Native Hawaiian or Other Pacific Islander | n (%) | n (%) | n (%) | n (%) |
| White | n (%) | n (%) | n (%) | n (%) |
| Multiple Races Checked | n (%) | n (%) | n (%) | n (%) |

^[1] Age calculated by determining the number of years between the date of informed consent and the date of birth. path\t program.sas date time

Programmer note Table 2.2 will be identical to Table 2.1 for the Safety Population.

Table 3 Abnormal Medical History at Baseline Safety Population

| De de Contant | VM202- 2 mg | VM202- 4 mg | VM202- 8 mg | VM202- 16 mg |
|----------------------------|-------------|-------------|-------------|--------------|
| Body System | (N=) | (N=) | (N=) | (N=) |
| Respiratory | n (%) | n (%) | n (%) | n (%) |
| Cardiovascular | n (%) | n (%) | n (%) | n (%) |
| Gastrointestinal | n (%) | n (%) | n (%) | n (%) |
| Hepatic | n (%) | n (%) | n (%) | n (%) |
| Endocrine/Metabolic | n (%) | n (%) | n (%) | n (%) |
| Central Nervous System | n (%) | n (%) | n (%) | n (%) |
| Hematopoietic/Lymphatic | n (%) | n (%) | n (%) | n (%) |
| Dermatological | n (%) | n (%) | n (%) | n (%) |
| Musculoskeletal | n (%) | n (%) | n (%) | n (%) |
| Genitourinary/Reproductive | n (%) | n (%) | n (%) | n (%) |
| Psychiatric | n (%) | n (%) | n (%) | n (%) |
| Alcohol/Drug Abuse | n (%) | n (%) | n (%) | n (%) |
| Drug Allergy | n (%) | n (%) | n (%) | n (%) |
| Non-Drug Allergy | n (%) | n (%) | n (%) | n (%) |
| Other | n (%) | n (%) | n (%) | n (%) |

Table 4
Peripheral Vascular Disease Intervention
Safety Population

| Intervention | VM202- 2 mg (N=) | VM202- 4 mg (N=) | VM202- 8 mg (N=) | VM202- 16 mg (N=) |
|---------------------------|----------------------|----------------------|----------------------|-----------------------|
| mervenion | (11-) | (11-) | (11-) | (11-) |
| PTA | n (%) | n (%) | n (%) | n (%) |
| Peripheral bypass | n (%) | n (%) | n (%) | n (%) |
| Amputation above the knee | n (%) | n (%) | n (%) | n (%) |
| Amputation below the knee | n (%) | n (%) | n (%) | n (%) |
| Atherectomy | n (%) | n (%) | n (%) | n (%) |
| Surgical bypass | n (%) | n (%) | n (%) | n (%) |
| Endarterectomy | n (%) | n (%) | n (%) | n (%) |
| Thrombectomy | n (%) | n (%) | n (%) | n (%) |
| Stent placement | n (%) | n (%) | n (%) | n (%) |
| Other | n (%) | n (%) | n (%) | n (%) |

Page 1 of x

Viromed Co., Ltd. Protocol Number: US-06-1-001

Table 5 Ulcer Measurement (cm²) [1] ITT Population

| | VM202- 2 | mg (N=) | VM202-4 | mg (N=) | VM202-8 | mg (N=) | VM202-10 | 5 mg (N=) |
|-------------------|--------------|--------------|--------------|--------------|--------------|--------------|--------------|--------------|
| | Result | Change [3] |
| Baseline [2] | | | | | | | | |
| N | n | | n | | n | | n | |
| Mean (SD) | xx.x (xx.xx) | | xx.x (xx.xx) | | xx.x (xx.xx) | | xx.x (xx.xx) | |
| Median | XX.X | | XX.X | | XX.X | | XX.X | |
| Min, Max | XX, XX | | xx, xx | | XX, XX | | xx, xx | |
| Day 15 (Pre-Dose) | | | | | | | | |
| Ň | n | n | n | n | n | n | n | n |
| Mean (SD) | xx.x (xx.xx) |
| Median | xx.x |
| Min, Max | XX, XX |
| Day 28 | | | | | | | | |
| Ň | n | n | n | n | n | n | n | n |
| Mean (SD) | xx.x (xx.xx) |
| Median | xx.x |
| Min, Max | XX, XX |
| Day 59 | | | | | | | | |
| Ň | n | n | n | n | n | n | n | n |
| Mean (SD) | xx.x (xx.xx) |
| Median | xx.x |
| Min, Max | XX, XX |
| | | | | | | | | |

path\t_program.sas date time

Programmer Note Repeat for all available time points.

^[1] Measurement taken was the largest contiguous area of ulceration.[2] Baseline defined as measurement taken most closely prior to first study drug administration.

^[3] Change= Change from Baseline

Viromed Co., Ltd. Page 1 of x Protocol Number: US-06-1-001

> Table 6 Ankle Brachial-Index (mmHg) ITT Population

| | VM202- 2 | mg (N=) | VM202-4 | mg (N=) | VM202-8 | mg (N=) | VM202-10 | 6 mg (N=) |
|-------------------|--------------|--------------|--------------|--------------|--------------|--------------|--------------|--------------|
| | Result | Change [2] |
| Index Limb | | | | | | | | |
| Right | n (%) | | n (%) | | n (%) | | n (%) | |
| Left | n (%) | | n (%) | | n (%) | | n (%) | |
| Delt | П (70) | | 11 (70) | | 11 (70) | | 11 (70) | |
| ABI Index Leg | | | | | | | | |
| Baseline [1] | | | | | | | | |
| N | n | | n | | n | | n | |
| Mean (SD) | xx.x (xx.xx) | | xx.x (xx.xx) | | xx.x (xx.xx) | | xx.x (xx.xx) | |
| Median | XX.X | | XX.X | | XX.X | | XX.X | |
| Min, Max | XX, XX | | XX, XX | | XX, XX | | XX, XX | |
| , | , | | , | | , | | , | |
| Day 15 (Pre-Dose) | | | | | | | | |
| Ň | n | n | n | n | n | n | n | n |
| Mean (SD) | xx.x (xx.xx) |
| Median | xx.x |
| Min, Max | XX, XX |
| | | | | | | | | |
| | | | | | | | | |
| ABI Non-Index Leg | | | | | | | | |
| Baseline [1] | | | | | | | | |
| N | n | | n | | n | | n | |
| Mean (SD) | xx.x (xx.xx) | | xx.x (xx.xx) | | xx.x (xx.xx) | | xx.x (xx.xx) | |
| Median | XX.X | | XX.X | | XX.X | | XX.X | |
| Min, Max | XX, XX | | XX, XX | | XX, XX | | XX, XX | |
| , | , | | , | | , | | , | |

^[1] Baseline defined as measurement taken most closely prior to first study drug administration.
[2] Change= Change from Baseline

Viromed Co., Ltd. Page 1 of x

Protocol Number: US-06-1-001

Table 7 Toe Brachial-Index (mmHg) ITT Population

| | VM202-2 | mg (N=) | VM202- 4 mg (N=) | | VM202-8 | mg (N=) | VM202-10 | 5 mg (N=) |
|-------------------|--------------|--------------|-------------------|--------------|--------------|--------------|--------------|--------------|
| | Result | Change [2] | Result | Change [2] | Result | Change [2] | Result | Change [2] |
| TBI Index Toe | | | | | | | | |
| Baseline [1] | | | | | | | | |
| N | n | | n | | n | | n | |
| Mean (SD) | xx.x (xx.xx) | | xx.x (xx.xx) | | xx.x (xx.xx) | | xx.x (xx.xx) | |
| Median | XX.X | | XX.X | | XX.X | | XX.X | |
| Min, Max | XX, XX | | xx, xx | | xx, xx | | XX, XX | |
| Day 15 (Pre-Dose) | | | | | | | | |
| N | n | n | n | n | n | n | n | n |
| Mean (SD) | xx.x (xx.xx) | xx.x (xx.xx) | xx.x (xx.xx) | xx.x (xx.xx) | xx.x (xx.xx) | xx.x (xx.xx) | xx.x (xx.xx) | xx.x (xx.xx) |
| Median | XX.X | XX.X | XX.X | XX.X | XX.X | XX.X | XX.X | XX.X |
| Min, Max | XX, XX | XX, XX | xx, xx | XX, XX | XX, XX | XX, XX | XX, XX | XX, XX |
| | | | | | | | | |
| TBI Non-Index Toe | | | | | | | | |
| Baseline [1] | | | | | | | | |
| N | n | | n | | n | | n | |
| Mean (SD) | xx.x (xx.xx) | | xx.x (xx.xx) | | xx.x (xx.xx) | | xx.x (xx.xx) | |
| Median | XX.X | | XX.X | | XX.X | | XX.X | |
| Min, Max | XX, XX | | xx, xx | | xx, xx | | xx, xx | |
| | | | | | | | | |

^[1] Baseline defined as measurement taken most closely prior to first study drug administration.

path\t_program.sas date time

Programmer Note For each measurement, repeat for all available time points.

^[2] Change= Change from Baseline

Table 8 Visual Analogue Scale for Pain (mm) ITT Population

| | VM202- 2 | mg (N=) | VM202-4 | mg (N=) | VM202-8 | mg (N=) | VM202-16 mg (N=) | |
|-------------------|--------------|--------------|--------------|--------------|--------------|--------------|-------------------|--------------|
| | Result | Change [2] | Result | Change [2] | Result | Change [2] | Result | Change [2] |
| Baseline [1] | | | | | | | | |
| N | n | | n | | n | | n | |
| Mean (SD) | xx.x (xx.xx) | | xx.x (xx.xx) | | xx.x (xx.xx) | | xx.x (xx.xx) | |
| Median | XX.X | | XX.X | | XX.X | | XX.X | |
| Min, Max | xx, xx | | xx, xx | | xx, xx | | xx, xx | |
| Day 15 (Pre-Dose) | | | | | | | | |
| Ň | n | n | n | n | n | n | n | n |
| Mean (SD) | xx.x (xx.xx) | xx.x (xx.xx) |
| Median | XX.X | XX.X |
| Min, Max | xx, xx | XX, XX |
| Day 28 | | | | | | | | |
| Ň | n | n | n | n | n | n | n | n |
| Mean (SD) | xx.x (xx.xx) | xx.x (xx.xx) |
| Median | XX.X | XX.X |
| Min, Max | xx, xx | XX, XX |
| Day 59 | | | | | | | | |
| N | n | n | n | n | n | n | n | n |
| Mean (SD) | xx.x (xx.xx) | xx.x (xx.xx) |
| Median | xx.x | XX.X |
| Min, Max | xx, xx | xx, xx |
| | | | | | | | | |

^[1] Baseline defined as measurement taken most closely prior to first study drug administration.

path\t_program.sas date time

Programmer Note Repeat for all available time points.

^[2] Change= Change from Baseline

Table 9
Transcutaneous Oxygen Pressure Assessment- TcPO₂ (mmHg)
ITT Population

| | VM202-2 | VM202-2 mg (N=) | | VM202-4 mg (N=) | | mg (N=) | VM202-16 mg (N= | |
|-------------------|--------------|-----------------|--------------|------------------|--------------|--------------|-----------------|--------------|
| | Result | Change [2] | Result | Change [2] | Result | Change [2] | Result | Change [2] |
| Anterior Calf | | | | | | | | |
| Baseline [1] | | | | | | | | |
| N | n | | n | | n | | n | |
| Mean (SD) | xx.x (xx.xx) | | xx.x (xx.xx) | | xx.x (xx.xx) | | xx.x (xx.xx) | |
| Median | XX.X | | XX.X | | XX.X | | XX.X | |
| Min, Max | XX, XX | | xx, xx | | XX, XX | | XX, XX | |
| Day 15 (Pre-Dose) | | | | | | | | |
| N | n | n | n | n | n | n | n | n |
| Mean (SD) | xx.x (xx.xx) | xx.x (xx.xx) | xx.x (xx.xx) | xx.x (xx.xx) | xx.x (xx.xx) | xx.x (xx.xx) | xx.x (xx.xx) | xx.x (xx.xx) |
| Median | XX.X | XX.X | XX.X | XX.X | XX.X | XX.X | XX.X | XX.X |
| Min, Max | XX, XX | xx, xx | xx, xx | xx, xx | XX, XX | xx, xx | xx, xx | xx, xx |
| | | | | | | | | |
| Posterior Calf | | | | | | | | |
| Baseline [1] | | | | | | | | |
| N | n | | n | | n | | n | |
| Mean (SD) | xx.x (xx.xx) | | xx.x (xx.xx) | | xx.x (xx.xx) | | xx.x (xx.xx) | |
| Median | XX.X | | XX.X | | XX.X | | XX.X | |
| Min, Max | XX, XX | | xx, xx | | xx, xx | | xx, xx | |
| | | | | | | | | |

^[1] Baseline defined as measurement taken most closely prior to first study drug administration.

path\t_program.sas date time

Programmer Note For each measurement, repeat for all available time points. Results for other measurements to be shown include Dosrum Foot and Chest..

^[2] Change= Change from Baseline

Protocol Number: US-06-1-001

Table 10 Subject Analgesic Use [1] ITT Population

| | VM202- 2 mg (N=) | VM202- 4 mg (N=) | VM202- 8 mg (N=) | VM202- 16 mg (N=) |
|------------------------------------|----------------------|----------------------|----------------------|-----------------------|
| Subject reported using analgesic d | uring study? | | | |
| Yes | n (%) | n (%) | n (%) | n (%) |
| No | n (%) | n (%) | n (%) | n (%) |

[1] Subject identified as having used analgesic based on whether subject reported using any concomitant medications considered to be an analgesic.

path\t_program.sas date time

Programmer Note:

Table 11 Study Drug Exposure Safety Population

| | VM202- 2 mg | VM202- 4 mg | VM202-8 mg | VM202- 16 mg |
|---|--------------|--------------|--------------|--------------|
| | (N=) | (N=) | (N=) | (N=) |
| | | | | |
| Day 1 Dose Administered? | | | | |
| | - (0/) | - (0/) | - (0/) | - (0/) |
| Yes | n (%) | n (%) | n (%) | n (%) |
| No, DLT from previous injection | n (%) | n (%) | n (%) | n (%) |
| No, Other | n (%) | n (%) | n (%) | n (%) |
| Zone of Injections | | | | |
| I | n (%) | n (%) | n (%) | n (%) |
| П | n (%) | n (%) | n (%) | n (%) |
| Ш | n (%) | n (%) | n (%) | n (%) |
| IV | n (%) | n (%) | n (%) | n (%) |
| V | n (%) | n (%) | n (%) | n (%) |
| VI | n (%) | n (%) | n (%) | n (%) |
| Total Volume Administered per Protocol? | | | | |
| Yes | n (%) | n (%) | n (%) | n (%) |
| No | n (%) | n (%) | n (%) | n (%) |
| Time Dose Administration (mg) | | | | |
| N | n | n | n | n |
| Mean (SD) | xx.x (xx.xx) | xx.x (xx.xx) | xx.x (xx.xx) | xx.x (xx.xx) |
| Median | XX.X | XX.X | xx.x | XX.X |
| Min, Max | xx, xx | xx, xx | xx, xx | xx, xx |
| Day 15 | | | | |
| Dose Administered? | | | | |
| Yes | n (%) | n (%) | n (%) | n (%) |
| No | n (%) | n (%) | n (%) | n (%) |
| 110 | 11 (70) | 11 (70) | 11 (70) | 11 (70) |
| | | | | |

Page 1 of x

Viromed Co., Ltd. Protocol Number: US-06-1-001

Table 12 Treatment Emergent Adverse Events by Cohort [1] Safety Population

| | VM202- 2 mg (N=) | | VM202- 4 mg (N=) | | VM202-8 | mg (N=) | VM202-16 mg (N=) | |
|---|-------------------|-----------|-------------------|-----------|--------------|-----------|-------------------|-----------|
| | Number of | Number of | Number of | Number of | Number of | Number of | Number of | Number of |
| System Organ Class / Preferred Term | Subjects [1] | Events | Subjects [1] | Events | Subjects [1] | Events | Subjects [1] | Events |
| Subjects Reporting at Least One Adverse Event | n (%) | n | n (%) | n | n (%) | n | n (%) | n |
| System Organ Class 1 | n (%) | n | n (%) | n | n (%) | n | n (%) | n |
| Preferred Term 1 | n (%) | n | n (%) | n | n (%) | n | n (%) | n |
| Preferred Term 2 | n (%) | n | n (%) | n | n (%) | n | n (%) | n |
| | | | | | | | | |
| • | | | | | | | | |
| System Organ Class 2 | n (%) | n | n (%) | n | n (%) | n | n (%) | n |
| Preferred Term 1 | n (%) | n | n (%) | n | n (%) | n | n (%) | n |
| Preferred Term 2 | n (%) | n | n (%) | n | n (%) | n | n (%) | n |

[1] At each level of summation (overall, system organ class, preferred term), subjects reporting more than one adverse event are counted only once.

Protocol Number: US-06-1-001

Table 13
Treatment Emergent Adverse Events by System Organ Class and Severity [1]
Safety Population
Part 1 of 2

| | VM202-2 mg (N=) | | | | | VM202-4 mg (N=) | | | | |
|--|-------------------------|-------------------------|-------------------------|-------------------------|-------------------------|-------------------------|-------------------------|-------------------------|-------------------------|-------------------------|
| System Organ Class / Preferred Term | Mild | Moderate | Severe | Life Threat. | Death | Mild | Moderate | Severe | Life Threat. | Death |
| Subjects Reporting at Least One Adverse Event | n (%) |
| System Organ Class 1 | n (%) |
| Preferred Term 1 | n (%) |
| Preferred Term 2 | n (%) |
| | | | | | | | | | | |
| - | | | | | | | | | | |
| System Organ Class 2 Preferred Term 1 Preferred Term 2 | n (%) n (%) n (%) |

^[1] At each level of summation (overall, system organ class, preferred term), subjects reporting more than one adverse event are counted only once using the highest severity.

Protocol Number: US-06-1-001

Table 13
Treatment Emergent Adverse Events by System Organ Class and Severity [1]
Safety Population
Part 2 of 2

| | VM202-8 mg (N=) | | | | | VM202-16 mg (N=) | | | | | |
|---|------------------|----------|--------|--------------|-------|-------------------|----------|--------|--------------|-------|--|
| System Organ Class / Preferred Term | Mild | Moderate | Severe | Life Threat. | Death | Mild | Moderate | Severe | Life Threat. | Death | |
